Patients without consistent access to a phone with text-messaging capabilities for the following seven days and/or without a primary care physician will be excluded from this study. Patients from the following groups will be excluded: pregnant, prisoners, did not speak English, were undergoing current chemotherapy, signs of jaundice, already received greater than 250 mL of IV fluids, or unable to provide informed consent.

D.2.b. Subject Recruitment Plans, Screening and Consent

Screening will begin as the patient checks in to the ED with the triage nurse and enters a chief complaint. Two RAs will monitor the emergency department electronic patient list in real time to identify patients with eligible chief complaints. The RA will approach the patient's provider to determine if patient meets inclusion criteria (2-4). If the provider determines the patient meets both inclusion criteria, the RA will approach the patient in his/her ED patient room to screen the patient for eligibility based on stated inclusion and exclusion criteria.

If patient meets all inclusion criteria and does not meet any exclusion criteria, the RA will discuss the study with the patient using a standard, IRB-approved script. If the patient is agreeable to participation in the study, written consent will be obtained and proof of research participation will be documented in the patient's electronic medical record.

D.2.c. Randomization Method and Blinding

Randomization of intervention will be 1:1 in randomized, permuted blocks.

Randomization will be performed in SAS (SAS Institute), version 9.4. Blinded allocation ("Drug 1" or "Drug 2") will be placed in sealed opaque envelopes labelled by subject ID before the enrollment period begins. All research team members involved in patient enrollment and outcome assessment (survey administration) will not be involved in this randomization process.

D.3. Intervention

Following randomization, a RA will work with the nursing staff to procure the correct IV solution and administer the solution. Times of initiation and termination of fluid administration and amount of actual fluid administered will be recorded for covariate analysis.

D.3.a. Description

Both intervention and control medications will be delivered intravenously via peripheral venous access at room-temperature. Fluid administration rate will be 1,000 mL/15 minutes by pressure bag method and will be monitored by an RA.

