At the time of enrollment, baseline characteristics of subjects will be collected by RAs by in-person interview (pre-intervention QoR-40 score) and from electronic medical record (age, gender). Some baseline characters will be collected at the chart abstraction (ED encounter disposition [discharged from ED/admitted to hospital/admitted to ICU], ED diagnosis type [by organ system]).

D.4.a. Primary Endpoint

The primary outcome of this study will be the post-treatment survey score of the Quality of Recovery-40 (QoR-40, see Attachment H-2) validated survey tool^{18,19}. The survey has been used extensively in the surgery anesthesia literature to measure patient-

reported recovery across five independent domains: Comfort, Emotion, Physical Independence, Patient Support, and Pain. Survey scores range from 40 to 200.

RAs will administer the QoR-40 to subjects initially before any intervention is administered (“pre”). Twenty-four hours following discharge, the RAs will administer the survey again by telephone (“post”). During survey administration, RA will fill-out survey on paper, and it will later be entered into the electronic database. If patient does not answer, two additional phone calls will be made in the 24-48 hours following ED discharge. Time of “post” survey response will be recorded.

D.4.b. Secondary Endpoint

Secondary endpoints are designed to examine differences in healthcare administration between the NS control and LR intervention groups. Secondary endpoints will be assessed at two time points (1) at the 24-hour post-discharge phone call and (2) with a 7-day follow-up text message utilizing a two-way text messaging system.

The following secondary endpoints will be recorded:

- (A) Sought additional healthcare for same complaint,
- (B) Returned to an ED for same complaint,
- (C) Filled an ED prescription from visit of enrollment, and

Each endpoint will be a dichotomous (yes/no) response. No adjudication of “same complaint” will be performed by the research team, as the intention is to capture the patient’s interpretation of healthcare utilization from the illness.

D.4.c. Subgroups

No *a priori* subgroup analyses are planned. Any subgroup analyses performed will be solely for the purpose of hypothesis generation.

E. Statistical Plan

E.1. Sample Size Determination and Power

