Sample size calculation was based on the detection of a 10-point difference on the QoR-40 survey scores. A 10-pt difference was selected as the minimum detectable difference maintaining clinical relevance, as supported by previous studies¹⁸⁻²¹. Sample size calculation ($\alpha = 0.05$, $\beta = 0.90$, 20% dropout, difference of 10 points) revealed a need for 156 total subjects.

E.2. Statistical Analysis

Baseline characteristics. Baseline characteristics will be reported with summary statistics as appropriate (mean, SD, median, IQR) and differences in characteristics will be conducted using t-test for continuous variables and chi-square test for categorical variables. If any baseline characteristics have significant differences, those behaviors will be reported in the results section and an adjusted analysis will be performed on primary and secondary variables to assess the impact of the imbalances.

Primary outcome. The primary outcome, pre-post difference in Quality of Recovery-40, will be analyzed using a t-test (if parametric) or Mann Whitney U Test (non-parametric) in an intention-to-treat (ITT) analysis. Due to the nature of emergency department

research, an additional analysis will be done by treatment received and compared to the primary ITT analysis.

Secondary outcome & safety analysis. Secondary outcomes will be reported as a relative risk with 95%CI in an ITT analysis. A safety analysis of selected secondary outcomes (return to ED and seeking additional healthcare for same complaint) will be performed by treatment received.

Covariate analysis. Differences in actual fluid administered and time from intervention to primary outcome will be assessed. If significant, analysis adjusting for covariates of time from intervention to primary outcome, post-QoR-40 administration, and amount of fluid (mL) received will be performed with multivariable linear regression and multivariable logistic regression (primary and secondary outcomes, respectively).

F. Quality Control

F.1. Study Monitoring Plan

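### Baseline significance tests decide whether a covariate-adjusted analysis is done; a short covariate set should be fixed in advance instead

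*Combined protocol and SAP*

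**What the plan says.** The baseline paragraph of E.2 says that "differences in characteristics will be conducted using t-test for continuous variables and chi-square test for categorical variables". The consequence of a positive test follows: "If any baseline characteristics have significant differences, those behaviors will be reported in the results section and an adjusted analysis will be performed". The sentence goes on to give the scope and purpose: "an adjusted analysis will be performed on primary and secondary variables to assess the impact of the imbalances".

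Section D.4 names the variables: "baseline characteristics of subjects will be collected by RAs by in-person interview (pre-intervention QoR-40 score) and from electronic medical record (age, gender"). It adds two items taken later at chart abstraction, ED disposition and ED diagnosis type, and also calls these baseline.

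The primary test in E.2 is an unadjusted t-test or Mann-Whitney test of the pre-post difference in QoR-40, by intention to treat. Secondary outcomes are reported as relative risks. On allocation, D.2.c says "Randomization of intervention will be 1:1 in randomized, permuted blocks" and names no stratification factor. No baseline covariate is pre-specified for any outcome. The only other adjustment rule, in the covariate paragraph of E.2, also depends on significance and concerns fluid volume and timing after randomisation.

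Two things are left open: the threshold for a significant difference, and whether the variables that reach it are the ones that enter the adjusted model. The second is the natural reading.

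**The concern.** If randomisation is sound, the null hypothesis for a variable fixed beforehand is known to be true. The test can only say how unusual the chance imbalance is. It is silent on the other thing that matters, namely how strongly the variable predicts QoR-40. A variable unrelated to recovery at p = 0.04 triggers an adjusted analysis, while a strong predictor at p = 0.06 does not.

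Three things follow. Whether a supplementary analysis appears is left to chance. A prognostic imbalance just short of the threshold stays in the unadjusted result. And the precision that known predictors could supply is given up in most trials, in a design that does not stratify.

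**Working it through.** **Inputs.** From E.1: alpha 0.05 (sidedness not stated), a printed beta of 0.90 read as power, and "20% dropout, difference of 10 points) revealed a need for 156 total subjects". From D.4: three variables collected at enrolment. Assumed: a baseline threshold of two-sided 0.05, independent baseline tests, and the correlations below. The documents give no SD and no correlation with the outcome.

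**The plan's own figure.** E.1 says "Sample size calculation was based on the detection of a 10-point difference on the QoR-40 survey scores", but without an SD the 156 cannot be reproduced forward, so I solved for the SD. With two-sided alpha, n per arm = 2 × (1.96 + 1.2816)² × SD² / 10². At SD 17.1 this is 61.4, rounded up to 62. Then 62 / 0.8 = 77.5, rounded up to 78 per arm, 156 in total. The implied SD is therefore about 17.1. Reading alpha as one-sided would imply about 18.9 to 19.0; reading power as 80% would imply 19.8. I use about 17 and 62 completers per arm.

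**How often the rule fires by luck.** 1 − 0.95³ = 0.143, or about 14%.

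**How large an imbalance escapes.** With 62 per arm, the largest non-significant standardised difference is 1.980 × √(2/62) = 0.356. For baseline QoR-40 at an assumed SD of 17, that is 0.356 × 17 = 6.0 points. With a pre-post correlation of 0.3 to 0.7, the post score would be displaced by 0.3 × 6.04 = 1.8 to 0.7 × 6.04 = 4.2 points. The change score would be displaced by the same range in the opposite direction, since it subtracts the whole baseline difference. The target difference is 10 points.

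**Conditional type I error of the unadjusted test.** Given a baseline imbalance z in a covariate with correlation ρ, the test statistic is distributed as N(ρz, 1 − ρ²). The error is the probability that it lies beyond ±1.96.

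| Imbalance | ρ = 0.3 | ρ = 0.5 |
|---|---|---|
| z = 0 | 4.0% | 2.4% |
| z = 1 | 5.0% | 4.8% |
| z = 1.9 (p = 0.057, not flagged) | 7.7% | 12.2% |

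Averaged over z, each column returns 5%. About 2% of trials have |z| between 1.8 and 1.96 for a given variable.

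**Power for 10 points** (62 per arm, SD 17.05). Power = Φ(10 / [SD × √(1 − R²) × √(2/62)] − 1.96).

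- Unadjusted: 10 / 3.062 = 3.266; power 90.4%.
- R² = 0.02: 10 / 3.031 = 3.299; power 91.0%.
- R² = 0.05: 10 / 2.985 = 3.350; power 91.8%.
- R² = 0.22 (three uncorrelated covariates: 0.3² + 0.3² + 0.2²): 10 / 2.705 = 3.698; power 95.9%. A simulation of 20,000 trials, which fits the model rather than using the normal approximation, gives 95%.

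In the same simulation, letting the adjusted result replace the unadjusted one whenever the rule fires gives power of 91% and overall type I error of 4.3%.

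**Disagreement on p < 0.05.** When the rule fires, adjusted and unadjusted results differ in about 8% of trials with no effect and 11% with a 10-point effect. Over all trials this is 0.14 × 0.08 = 1.1% to 0.14 × 0.11 = 1.5%.

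**The case against.** The strongest reply is that the plan already says which result counts. E.2 refers to the intention-to-treat comparison as the primary analysis and gives the adjusted analysis the purpose of gauging the imbalances. This stands. A reader might infer that the report would carry two competing answers with nothing to choose between them; the text does not support that. Nor does it support an inference that the rule inflates overall type I error: the unadjusted randomised comparison is valid, and the simulated error stays below 5% even if the adjusted result took over.

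A reader might also count all five characteristics in D.4 and put the chance of a trigger at 1 − 0.95⁵ = 23%. That does not follow. Disposition and diagnosis type come from chart abstraction, and disposition may be settled after the infusion, so a difference there need not be chance.

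For pre-intervention QoR-40 it can be said that the change score in E.2 already brings baseline in. That is partly right. The change score over-corrects when the correlation is below 1, D.4.a defines the endpoint as the post score, which has no correction, and neither does anything for age or gender.

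Finally, the power gain depends on assumed correlations. It is about 1 point if the covariates explain 2% to 5% of the variance. Much of any larger gain probably comes from baseline QoR-40. This limits the size of the point, not its direction.

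**Conclusion.** The point holds as one of conditional bias and lost precision; the planned primary test remains valid. The plan lets a test that cannot inform the decision determine whether an adjusted analysis is done. The rule fires by luck in about 14% of trials, given independent tests at 0.05 on three variables. When it stays silent on a near-miss in a prognostic variable, the unadjusted test has a conditional error of roughly 8% to 12% at z = 1.9, and less than 5% when the arms are balanced. The power forgone is between about 1 and 5 percentage points for R² from 0.02 to 0.22. Disagreement between the two analyses would be rare, about 1% to 2% of trials. All the conditional and power figures rest on an SD of about 17, inferred from the sample size, and on correlations that the documents do not give.

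**What to change.** In E.2, delete the baseline significance tests and the trigger that depends on them, and report baseline characteristics descriptively by arm. Pre-specify adjustment for pre-intervention QoR-40, age and gender, whatever the observed imbalance:

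- **Primary outcome:** a linear model for QoR-40 with treatment and these three covariates. With baseline QoR-40 in the model, the treatment estimate is the same for the post score and the change score, so the difference between D.4.a and E.2 no longer affects it.
- **Secondary outcomes:** a model that yields an adjusted relative risk, such as modified Poisson regression with robust standard errors.
- **Status:** state that the adjusted analysis is primary and the unadjusted test is the sensitivity analysis.
- **Exclusions:** keep ED disposition, and any other variable determined after randomisation, out of the covariate set.
- **Chief complaint:** it is known at screening, but D.2.a lists the complaints without grouping them. Add it only if the grouping is defined beforehand.

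All three covariates are already collected, so the change is to the wording of the analysis plan. The statistical cost is a few degrees of freedom. The gain may be small if the covariates turn out to be weak predictors.

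### The primary outcome is the post-treatment QoR-40 score in D.4.a but the pre-post change in E.2, and the choice of test has no criterion

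*Combined protocol and SAP*

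**What the plan says.** Section D.4.a (Primary Endpoint): "The primary outcome of this study will be the post-treatment survey score of the Quality of Recovery-40". The same section gives the scale: "Survey scores range from 40 to 200". It also describes one administration before treatment and one by telephone 24 hours after discharge.

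Section E.2 (Primary outcome): "The primary outcome, pre-post difference in Quality of Recovery-40, will be analyzed using a t-test (if parametric) or Mann Whitney U Test". E.2 goes on to refer to this as the primary analysis: "an additional analysis will be done by treatment received and compared to the primary ITT analysis". It does not say how the data are to be judged parametric, by whom, or when.

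Section E.1: "Sample size calculation was based on the detection of a 10-point difference on the QoR-40 survey scores". This fits either definition. The aim in C.1 concerns quality of recovery 24 hours after discharge and does not mention change.

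Baseline QoR-40 is available for adjustment. Section D.4 says that "baseline characteristics of subjects will be collected by RAs by in-person interview (pre-intervention QoR-40 score" among other items. E.2 uses it for adjustment only if a baseline comparison is significant, when "an adjusted analysis will be performed on primary and secondary variables to assess the impact of the imbalances". E.2 also has a separate covariate analysis triggered by a significant difference in fluid volume or timing: "If significant, analysis adjusting for covariates of time from intervention to primary outcome, post-QoR-40 administration, and amount of fluid (mL) received".

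**The concern.** Two current sections each define the primary outcome, and they define different variables. Neither is superseded text, and nothing in the document ranks one section above the other.

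The two estimates differ by exactly the chance baseline difference between the arms. With the same data, one can be significant and the other not. They also have different power, unless the pre-post correlation is about 0.5 with equal SDs.

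E.2 adds further routes to a headline result. It has a choice of test with no criterion, where the t-test addresses a mean difference in points and the Mann-Whitney test compares ranks. It also has two regressions triggered by significance tests, one of which uses variables measured after randomisation. The plan does not say that this second regression cannot replace the primary result. A report could present any of several analyses and cite the protocol accurately for it.

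A separate point is an improvement and not an error. The unadjusted change score fixes the baseline coefficient at 1, which is generally less precise than estimating it.

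**Working it through.** **Inputs from the documents.** N = 156, 1:1 allocation, 20% dropout, 10-point difference, alpha 0.05.

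**Assumptions.** The test is two-sided. E.1's β = 0.90 is read as 90% power. Pre and post SDs are equal unless stated. The correlation ρ is 0.3, 0.5 or 0.7. The documents give neither an SD nor ρ.

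**Step 1: the plan's own figure.** N = 156 cannot be reproduced without an SD, so I solved for the SD it implies. Evaluable per arm: 156 × 0.8 / 2 = 62.4, taken as 62. From the noncentral t distribution, 90% power for 10 points needs SD = 17.04. If dropout was added by multiplying by 1.2, there are 156 / 1.2 / 2 = 65 per arm and SD = 17.45. If the test was one-sided, SD = 18.92. The implied SD does not show whether a single score or change was meant, so both readings are carried below.

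**Step 2: why the two estimates differ.** Let X be the baseline score and Y the 24-hour score, in subjects with both.

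- Post-score estimate: mean Y(LR) − mean Y(NS).
- Change estimate: [mean Y(LR) − mean Y(NS)] − [mean X(LR) − mean X(NS)].

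The gap between them is the baseline difference. Its standard error is 17.04 × √(2/62) = 3.06, so its mean absolute size is 3.06 × √(2/π) = 2.44 points. Baseline adjustment is triggered only beyond about 1.98 × 3.06 = 6.06 points. A gap above 5 points (half the target, an illustrative threshold) that triggers no adjustment occurs in about 5% of trials. Across the SD-ratio and correlation scenarios this runs from 0% to 16%.

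**Step 3: power.** With single-score SD s, the SD of change is s√(2(1−ρ)) and the residual SD after regression on baseline is s√(1−ρ²). Example at ρ = 0.3, s = 17.04: change 17.04 × √1.4 = 20.16; regression 17.04 × √0.91 = 16.26.

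| Reading of SD 17.04 | ρ | Post t-test | Change t-test | Regression on baseline |
|---|---|---|---|---|
| Single score | 0.3 | 90.0% | 78.2% | 92.5% |
| Single score | 0.5 | 90.0% | 90.0% | 96.3% |
| Single score | 0.7 | 90.0% | 98.7% | 99.5% |
| Change | 0.3 | 97.0% | 90.0% | 98.0% |
| Change | 0.5 | 90.0% | 90.0% | 96.3% |
| Change | 0.7 | 70.9% | 90.0% | 94.0% |

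The variance ratio of regression to change is (1−ρ²)/(2(1−ρ)) = (1+ρ)/2, which is 0.65, 0.75 and 0.85.

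**Step 4: disagreement on significance.** Simulated with bivariate normal data and a true difference of 10.

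| Comparison | Reading of SD | ρ 0.3 | ρ 0.5 | ρ 0.7 |
|---|---|---|---|---|
| Post vs change t-test | Single score | 19% | 13–14% | 10% |
| Post vs change t-test | Change | 10% | 14% | 28% |
| t-test vs Mann-Whitney on change | Single score | 5% | 3% | 1% |
| t-test vs Mann-Whitney on change | Change | 3% | 3% | 3% |

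**Step 5: worst-case false positives.** If the more favourable result were reported under the null, the rate would be about 9% for post or change t-test. For t-test or Mann-Whitney on change it would be about 6%, with normal or bounded skewed data.

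**Step 6: one model covers both definitions.** Regressing Y, or Y − X, on arm and X gives the same arm coefficient; only the coefficient on X shifts by 1. In one simulated data set both versions gave an estimate of 7.314, SE 2.538 and p = 0.0047.

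**The case against.** The strongest reply is that the documents lean one way. Only E.2 assigns a test, it assigns it only to change, and it calls that the primary analysis. D.4.a could be read as naming the instrument and its timing, so that one phrase in D.4.a would repair the conflict. This reduces the ambiguity but does not remove it. D.4.a is the endpoint section, it describes both administrations, and it still names the post-treatment score. The aim also speaks only of recovery at 24 hours.

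The second reply is that the choice of test is nearly harmless if it is applied as a rule. With a Shapiro-Wilk check at 0.05 deciding the test, simulated type I error was 5.0% to 5.2%, including with bounded skewed scores. That stands. The 6% and 9% figures describe selection by result, which the plan does not authorise. The missing criterion is a smaller defect than the endpoint conflict.

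Third, regression is neither of E.2's named tests, and its gain depends on an undocumented correlation. At ρ = 0.7 with a single-score SD it raises power only from 98.7% to 99.5%. Robust standard errors are a precaution, because no failure of ordinary ones under skew was shown. All of this is fair. Regression reconciles the two endpoint definitions, but E.2's test wording must be rewritten to use it.

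Finally, E.2 describes the baseline-imbalance adjustment in terms that suggest a sensitivity analysis. That is also fair. The covariate analysis on fluid volume and timing has no such label.

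**Conclusion.** The concern holds, and the endpoint conflict must be fixed before analysis. D.4.a and E.2 define different primary outcomes, and no other section resolves it. Under the assumptions above, the two t-tests would reach different conclusions on significance in about 10% to 28% of trials with a true 10-point effect. The power of the analysis not used for sizing could be anywhere from 71% to 99%. These ranges rest on an SD inferred from N = 156 and on assumed correlations. The contradiction itself rests on the text alone.

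Neither analysis is biased. The unspecified test criterion matters less, with disagreement in 1% to 5% of trials. Baseline adjustment is a recommended gain in precision and does not correct an invalid method.

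**What to change.** **Required.** Make D.4.a and E.2 name the same single primary analysis, with one test.

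**Recommended form.** Use linear regression of the 24-hour QoR-40 score on randomised arm, adjusted for baseline QoR-40, by intention to treat. Report the adjusted mean difference, 95% CI and p-value. Robust (HC3) standard errors are a reasonable safeguard for a bounded score; in simulation they cost under 1 percentage point of power and kept type I error at 4.6% to 5.0%. Use this model whatever the distribution, delete the choice between parametric and non-parametric tests, and keep Mann-Whitney as a sensitivity analysis.

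**Also state:**
- in E.2, that the baseline-imbalance adjustment and the covariate analysis on fluid volume and timing are sensitivity or exploratory analyses and never replace the primary result;
- in E.1, that the 10 points are the between-arm mean difference on this endpoint.

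**Cost.** Wording in D.4.a, E.1 and E.2, and one regression. No new data are needed.

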STUDY PROTOCOL

Saline vs. Lactated Ringers for Emergency Department IV Fluid Resuscitation

NCT03133767

Date Created: 03/15/17

Date Uploaded: 06/26/18

A. Introduction

A.1. Health Problem Needing Intervention and Impact of Proposed Intervention

Administration of intravascular (IV) fluid is the most common emergency department (ED) procedure¹. IV fluids are integral to increasing effective blood volume and ensuring organ perfusion in patients with volume depletion and dehydration². There are many options of IV fluids providers can use when treating ED patients³. Surveys show physicians do not cite an evidence-based reason for selecting the crystalloid IV fluid used; the decision was likely to be influenced by type and location of practice^{4,5}. A gap exists in the current literature, as there is no evidence for the optimal IV fluid choice for the ED patient requiring IV fluid before discharge.

Normal saline (NS) is commonly used as an IV fluid replacement in ED patients⁶. However, NS has been associated with increased risk of acidosis and acute kidney injury. This study will use a novel approach of a patient-centered outcome in a non-critically ill population to ascertain the optimal IV fluid for patient quality of recovery. The results of this study will inform provider's IV fluid decisions between NS and LR. More importantly, the results of this study will have the power to improve patient's quality of recovery following IV fluid administration and subsequent ED discharge.

B. Background

B.1. Prior Literature and Studies

Common IV fluids used for ED patients are normal saline (NS), a 0.9% sodium chloride solution, and lactated ringer's (LR), another isotonic saline solution³. There is a wealth of literature comparing IV crystalloid solutions, like NS and LR, among others⁷⁻⁹, yet administration of LR and NS by ED providers remains heterogeneous for non-critical ED patients.

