Intervention is 2,000 mL lactated ringer's IV solution (see description below).

"Each 100 mL of Lactated Ringer's Injection, USP contains sodium chloride 600 mg, sodium lactate, anhydrous 310 mg, potassium chloride 30 mg and calcium chloride, dihydrate 20 mg... A liter provides 9 calories (from lactate), sodium (Na⁺), 130 mEq, potassium (K⁺) 4 mEq, calcium (Ca⁺⁺) 3 mEq, chloride (Cl⁻) 109 mEq and lactate [CH₃CH(OH) COO⁻] 28 mEq. The electrolyte content is isotonic (273 mOsmol/liter, calc.) in relation to the extracellular fluid (approx. 280 mOsmol/liter). The pH of the solution is 6.6 (6.0 to 7.5)."¹⁷

Control is 2,000 mL of normal saline (0.9% sodium chloride).

D.3.b. Subject Compliance Monitoring

RAs will record time of initiation and completion of each bag of IV fluid and confirm patient is receiving correct fluid for allocation group. Any crossovers or premature stopping of fluid administration will be documented. Actual amount of fluid (mL) received will be documented.

D.3.c. Data Collection Procedures for Adverse Events

Any adverse event occurring in the ED would be recorded by the RA. Subjects will also be given contact information for a study physician, trained in emergency medicine, and will be instructed to call with concerns or to report any adverse events.

Further, an EM physician, not affiliated with the study, will be presented group data (blinded to treatment allocation) of 28-day patient medical treatment at the enrolling medical facility to assess safety for stopping. This chart review data will be collected by a research team member, blinded to subject group. Subject group ("A" or "B") will be added by study statistician (treatment ["LR" or "NS"] will not be revealed).

D.4. Study Outcome Measurements and Ascertainment

Outcomes will be recorded by trained RAs at time of ascertainment. RA obtaining outcome measurement will be blinded to subject allocation. Data will be entered and stored electronically on a secure server that can be accessed from any location at the enrolling site. Paper surveys will be saved in a locked file cabinet at the enrolling site.

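### The one safety analysis in E.2 counts only visits the patient attributes to the same complaint, and no by-arm analysis of adverse events or other visits is specified

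*Combined protocol and SAP*

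**What the plan says.** E.2, under secondary outcome and safety analysis, has one sentence on safety: "A safety analysis of selected secondary outcomes (return to ED and seeking additional healthcare for same complaint) will be performed by treatment received". It names no estimate, test or interval for this analysis.

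D.4.b defines the two outcomes: "A) Sought additional healthcare for same complaint" and "B) Returned to an ED for same complaint". It adds: "Each endpoint will be a dichotomous (yes/no) response". No adjudication of the same-complaint judgement "will be performed by the research team, as the intention is to capture the" patient's own reading of care used for the illness. Both items are collected at the 24-hour call and in the 7-day text, and the procedure table in H.1 repeats the same-complaint wording.

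Other safety provisions lie outside E.2:

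- **D.3.c:** research assistants record adverse events in the ED. Subjects receive a study physician's contact details and "will be instructed to call with concerns or to report any adverse events". An emergency physician outside the study is shown 28-day treatment at the enrolling facility by group A or B, to judge safety for stopping.
- **H.1:** adverse-event monitoring is marked during the infusion, at the call, at the text and at the 28-day chart review.
- **F.1:** safety reports follow every 30 subjects. A recorded event goes to the Safety Coordinator within 24 hours, and the IRB is notified.

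**The concern.** The two outcomes were written to describe healthcare use for the presenting illness. E.2 reuses them for safety without changing their definition. They then mainly track whether the original illness persisted or came back, which is a different question from whether the fluid caused a new problem.

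Section A.1 gives a reason to care about new problems, since it says that "NS has been associated with increased risk of acidosis and acute kidney injury". A patient enrolled for diarrhea who later seeks care for something they regard as separate can truthfully answer no to both items. If such visits differed between the fluids, the E.2 comparison would not include them, and no other analysis in E.2 would. A reader of the results could take a neutral safety comparison as covering more than it does.

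**Working it through.** **1. Does the restriction apply to both outcomes?** In E.2 the phrase about the same complaint could be read as attaching only to seeking healthcare. D.4.b settles this, because its ED item is "Returned to an ED for same complaint", and H.1 uses the same restriction. Both outcomes are limited.

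**2. What can enter the comparison?** For one arm, let p be the proportion with a same-complaint visit, q the proportion with only a visit for another problem, and s the share of the q group who nevertheless call it the same complaint.

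- Expected proportion answering yes = p + s × q.
- Expected relative risk = (p1 + s × q1) / (p0 + s × q0).
- If s = 0, this is p1 / p0, and q1 and q0 drop out whatever their size.
- If s is above 0, part of the difference enters, in an amount set by unadjudicated labelling.

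The documents give no value for p, q or s, so the loss cannot be sized.

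**3. Do the other provisions supply the missing comparison?**

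| Provision | Limited to same complaint? | Compared by arm? | Limits |
|---|---|---|---|
| E.2 safety analysis | Yes | Yes, by treatment received | 24 hours and 7 days; patient's judgement |
| D.3.c group review | No | Yes, as A and B | Enrolling facility only; for stopping; no measure or reporting stated |
| H.1 adverse-event monitoring | No | None stated | Content of the enquiry at the call and text not described |
| F.1 event review | No | None stated | Case by case |

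The ED item in D.4.b covers any ED, while the D.3.c review covers one facility. A new-problem visit elsewhere falls outside both. It would be seen only if reported as an adverse event, and E.2 has no analysis of those.

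**4. How precise would a wider comparison be?** The plan gives no size or power for safety. Its only figure is 156 in total, for the primary outcome. That cannot be reproduced because no SD is stated. Reading the printed β of 0.90 as power, with two-sided α of 0.05, an SD of about 17.1 would give it:

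- 2 × (1.96 + 1.282)² × 17.1² / 10² = 61.5, so 62 per arm.
- 62 / 0.8 = 77.5, so 78 per arm, or 156.

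Nothing below depends on that SD. Per arm there are 156 / 2 = 78 randomized, and 78 × 0.8 = 62.4, about 62, after 20% dropout.

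The 95% CI is RR × exp(±1.96 × SE), with SE = √[(1 − a)/(n × a) + (1 − b)/(n × b)]. All rates here are assumptions used only to judge precision:

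- a = b = 10%: RR 1.00, CI 0.39 to 2.56 at n = 78 and 0.35 to 2.88 at n = 62.
- a = 16%, b = 8%: RR 2.00, CI 0.81 to 4.96 at n = 78 and 0.72 to 5.54 at n = 62.

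**5. Would pooling all visits dilute a difference?** Assume same-complaint visits of 10% in both arms and new-problem visits of 10% against 2%. Power at two-sided 5% = Φ[(|d| − 1.96 × pooled SE) / unpooled SE].

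- Any reason (20% against 12%): 27% at n = 78 and 23% at n = 62.
- New problem alone (10% against 2%): 56% and 47%.

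Pooling about halves the power in this example, so the two kinds of visit should be shown separately.

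**The case against.** The strongest reply is that safety is covered elsewhere, and against four tempting inferences it succeeds.

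- **That this is the only safety comparison in the whole plan.** It is the only one in E.2. D.3.c plans a review by group that is not limited to the same complaint.
- **That patients are never asked about other events.** D.4.b is a list of secondary endpoints, so an adverse-event question would not be expected there. H.1 marks monitoring at both contacts. Its content is undescribed, which is not the same as absent.
- **That a fluid-related harm is always recorded as no, or cannot be shown.** Nothing in the documents says how such a harm would present. Eligible complaints include nausea, dizziness, weakness and fatigue, and the patient decides what matches. Under the assumed rates in step 5, the expected same-complaint RR would be 0.125 / 0.105 = 1.19 if a quarter of new-problem visits were labelled the same complaint, and 0.15 / 0.11 = 1.36 if half were.
- **That the trial will declare the two fluids equally safe.** No equivalence or non-inferiority claim on safety is stated. The hypothesis concerns quality of recovery, and the secondary aim is descriptive.

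It is also fair to say that a wider endpoint would seldom settle the matter at this sample size.

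What the reply does not answer is the analysis gap. The D.3.c review has no stated measure and is not said to be reported, and E.2 provides no by-arm account of adverse events or of visits for other reasons.

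**Conclusion.** The point holds as a limit of the analysis specified in E.2. Both safety outcomes depend on the patient attributing the visit to the presenting complaint, so visits seen as new problems can be left out, and no specified and reported by-arm analysis picks them up. This follows from the definitions and needs no assumed rate.

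The size is unknown. The documents give neither visit rates nor any basis for how patients would label them, so no figure for missed harm is offered. The intervals above show only that the wider comparison would be imprecise, which bears on how to report it. The gap is worth closing because the contacts and the chart review are already planned. It does not mean that safety is unmonitored.

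**What to change.** - **Collection (D.4.b, H.1).** At the 24-hour call and in the 7-day text, ask first whether the patient has been to any ED or sought other healthcare for any reason, then whether it was for the same complaint. State how adverse events are asked about at these contacts.
- **Endpoints (D.4.b).** Keep the same-complaint versions unchanged as the utilization endpoints.
- **Analysis (E.2).** Define the safety analysis as a tabulation by treatment received of any-reason visits, split into same-complaint and new-problem visits, together with recorded adverse events and visits found in the 28-day chart review. Give counts and, where useful, a relative risk with its 95% CI, and label the result descriptive.

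The cost is one extra question at two existing contacts and one more table, partly from data already to be collected. Any-reason visits will include unrelated events that dilute the relative risk, which is why the split is needed, and intervals will be wide at 156 subjects. Nothing here alters treatment or the review for stopping.
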